Patients will be randomized 1:1 to receive either standard of care (catheter removal with no bladder irrigation) or bladder irrigation with 2% povidone-iodine solution immediately prior to catheter removal. Randomization envelopes will be provided by the biostatistician and stored in a secure location in Urology Research. At the time research staff contact the pharmacist with the Betadine request, group assignment will be verified.

The first group will receive standard of care (SOC) only (indwelling catheter removal without any other interventions). If the patient is randomized to the SOC arm, the research nurse will simply remove the indwelling catheter. The second group will receive a single dose of approximately 60 cc of 2% povidone-iodine (Betadine) placed into the bladder. When the patient is randomized to the Betadine rinse arm, the research pharmacist will be contacted. The pharmacist will prepare and deliver the Betadine filled syringe to the research staff for instillation. The Betadine solution will be instilled through the catheter and left to dwell for 10 minutes, drained, and then the catheter will be removed. Research staff will be trained by a physician to remove the catheter using aseptic technique and prevent introduction of bacteria. To ensure patients are able to adequately void after catheter removal, designated study personnel (Urologists), will manage the study patient's voiding trial.

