48-72 hours after catheter removal a urine sample will be obtained to repeat UA and UC. If enrolled patients are still inpatient at this time point, study staff will see the patient in the hospital and conduct the Visit 2 activities. If the patient has been discharged from the hospital, this visit will occur in the Urology Research office. While not ideal or preferred, if the patient is not available for an in-person visit, the questionnaire may be completed over the phone, or sent to the patient and returned by mail (returned by USPS, email, or fax). In addition to the UA and UC, the UTISA questionnaire will also be completed. The UTISA questionnaire is a validated tool which will be utilized to assess the "severity" and "bothersomeness" of the most frequently reported signs and symptoms of uncomplicated UTI⁸. The Beaumont laboratory will evaluate all collected specimens. If a patient develops symptoms suggestive of a UTI, then further testing may be performed at the discretion of their managing physician or one of the study investigators. Research staff will also contact patients by phone at 7 and 28 days after catheter removal. At that time the UTISA will be administered to assess urinary symptoms, including diagnosed UTIs since the time of catheter removal. The UTISA may be completed verbally over the phone or by mail (returned by USPS, mail, or fax). If the patient's responses indicate a possible UTI, the patient will be referred to their primary care provider and/or other health care provider for evaluation.

Patients requiring reinsertion of an indwelling catheter prior to study completion will be withdrawn from the study. Patients that do not comply with the study protocol may also be withdrawn from the study by the Principal Investigator (PI).

	Screening & Treatment Visit Inpatient Visit	Visit 2 48-72 Hours Clinic or Inpatient Visit	Visit 3 7 ± 3 days Phone Call	Visit 4 28 ± 3 days Phone Call
Informed Consent	Х			
Review Inclusion and Exclusion Criteria	Х			
Review of Current Antibiotic Medication Use	Х	Х	X	Х
Urine collection: UA & UC	Х	Х		
UTISA Questionnaire		Xa	Xb	Xb
Indwelling Catheter Removal	Х			
Betadine Bladder Irrigation	Xc			
Assess for Adverse Events	Х	Х	X	Х

SCHEDULE OF ACTIVITIES

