^aAt Visit 2 the UTISA may be completed in person, over the phone, or by mail (returned via USPS, email, or fax). ^bAt visits 3 and 4 the UTISA may be completed over the phone or by mail (returned via USPS, email, or fax). ^cBetadine Bladder Irrigation will only be completed with those patients who are randomized to the treatment group.

IV. RISKS AND BENEFITS

Potential Benefits: This intervention may be beneficial for both patients and the hospital. The rate of hospital acquired CAUTIs may be reduced without increasing the risk of antimicrobial resistance.

Potential Risks:

Risks of Urinary Catheterization:

Less Frequent (occurring from 1% to 10% of the time):

- Temporary inability to urinate
- Bleeding
- Mild cramping
- Urinary tract infection

Risks of Betadine:

Less Frequent (occurring from 1% to 10% of the time):

• Local irritation of the bladder

Rare (occurring less than 1% of the time):

• Allergic reaction

Unknown Risk:

• Brown discoloration of urine

Risks of Bladder Irrigation:

Less Frequent (occurring from 1% to 10% of the time):

• Discomfort while the indwelling urinary catheter is clamped

All patients will be closely monitored by the research staff during the instillation, if applicable, and during catheter removal. All unanticipated problems will be reported to Beaumont's Investigational Review Board (IRB) per policy.

V. COMPENSATION

Patients will be reimbursed for time and travel during the course of the study, as outlined in the table below. Stipend checks will be sent, via US mail, in the amount listed below after each completed visit which is eligible to receive a stipend. If patients are unable to complete all study visits, they will be paid only for the visits they were able to complete.

Visit	Stipend Per Visit
Screening and Treatment Visit	\$25.00
Study Visit 2	\$25.00
Study Visit 3	\$0.00
Study Visit 4	\$0.00
Maximum Total (if all visits are included)	\$50.00

VI. ELIGIBILITY CRITERIA

Inclusion:

- 1) Provide written informed consent and the willingness and ability to comply with all aspects of study requirements
- 2) Male
- Inpatients ≥ 18 years of age with an indwelling catheter in place for at least 5 days with a plan for removal

Exclusion:

- 1) Patients planned for discharge with an indwelling catheter in place
- 2) Patients unable to report urinary symptoms accurately
- 3) Patients with hyper-sensitivity or allergic reaction to Betadine, iodine, shellfish or other related compounds

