- 4) Clinical signs or symptoms of urinary tract infection at the time of consent
- 5) Patients currently being treated for UTI
- 6) Patients currently taking any antibiotic medication, other than those listed in Appendix B
- 7) Patients already taking medications known to potentially irritate the bladder, such as, but not limited to, cyclophosphamide, ifosfamide, and other chemotherapeutic agents
- 8) Patients with history of bladder cancer, pelvic radiation or interstitial cystitis
- 9) Patients unable to comply with study requirements
- Any other condition which, per investigators' judgment, may increase patient risk and/or impede the reliability of study data

VII. DATA ANALYSIS

An infection rate of 25% is anticipated at day 2 post catheter removal for the SOC group. A difference has been shown of a 75% drop in infection rate using povidone-iodine bladder irrigation⁵. A power analysis using these estimates yields 55 patients needed in each arm to have 80% power at a 0.05 significance level to detect a difference of 25% versus 6.25%. We estimate at most a 10% dropout rate and plan to enroll 60 patients per arm to account for this.

Descriptive statistics will be provided for all data collected. Categorical variables will be reported as counts and percent frequencies. All continuous variables will be reported as means

+/- the standard deviation followed by the median, minimum to maximum or the median (25th, 75th percentiles) then minimum to maximum dependent on the normality of the data.

The endpoint of presence or absence of bacteriuria at 48-72 hours post catheter removal will be examined with a Fisher's exact tests, odds ratio and 95% confidence intervals. If any differences are found in what appear to be confounders for UA, a multivariate logistic regression analysis may be completed adjusting for these differences.

The categorical variables will be examined using Pearson's Chi-square tests where appropriate (expected frequency >5), otherwise Fisher's exact tests will be used. Continuous variables will be examined for normality. Normally distributed variables will be analyzed using t-tests. Non-normally distributed variables will be examined using non-parametric Kruskal-Wallis tests.

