REDCap (Research Electronic Data Capture) is the web-based software program that will be utilized for data collection and management. Urology Research will be responsible for all data management responsibilities including, but not limited to, database creation, data entry and query resolution. Data analyses will be performed by a Beaumont Biostatistician utilizing statistical software.

VIII. DATA SAFETY MONITORING PLAN

Ongoing safety monitoring will be performed by the study staff, including the PI and coinvestigators. The PI will have ultimate responsibility of assuring patient safety. A Medical Safety Monitor (MSM) will be assigned by the PI. The MSM will be a physician who is not involved in the study and who has no conflict of interest. The MSM will review Serious Adverse Events (SAEs) and will determine expectedness and causality of the event. The MSM may suggest protocol modifications to prevent the occurrence of adverse events (e.g., modifying the protocol to require frequent measurement of laboratory values predictive of the event or to improve expeditious identification of SAEs). If the MSM is unavailable for an extended period (i.e. extended vacation, illness, etc.) a back-up MSM will be nominated by the study PI. Safety issues will also be addressed in the annual reports to Beaumont's IRB. Additional data safety monitoring procedures include:

- Research Administration's Clinical Research Quality and Process Improvement Program (CRQIP) will perform in-house monitoring of the first patient enrolled after the completion of visit 1
- Safety data review at study team meetings

IX. REFERENCES

- Warren, J. W., Platt, R.J., Rosner, B., & Kass, E. H. (1978). Antibiotic irrigation and catheterassociated urinary-tract infections. *New England Journal of Medicine*, 299, 570-573. doi:10.1056/NEJM197809142991103

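### Men who need a catheter reinserted leave the whole study, so as written they have no scheduled adverse-event assessment afterwards, and no rule requires reinsertions to be recorded or reported by arm.

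*Combined protocol and SAP*

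**What the plan says.** The rule stands in Section III (Methodology), just before the Schedule of Activities: "Patients requiring reinsertion of an indwelling catheter prior to study completion will be withdrawn from the study". It is mandatory, whereas the next sentence, on non-compliance, leaves withdrawal to the investigator's discretion. It removes the man from the study, not just from the 48-72 hour endpoint.

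The row "Assess for Adverse Events" in the Schedule of Activities is marked at all four visits: treatment, 48-72 hours, day 7 ± 3 and day 28 ± 3. The last two are telephone contacts: "Research staff will also contact patients by phone at 7 and 28 days after catheter removal". The table has no early-termination visit.

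Section IV (Risks and Benefits) lists "Temporary inability to urinate" among the risks of catheterisation and "Local irritation of the bladder" among the risks of Betadine, each at 1% to 10%. Section III puts study urologists in charge of voiding: "To ensure patients are able to adequately void after catheter removal, designated study personnel (Urologists), will manage" each man's voiding trial.

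Section VII (Data Analysis) says: "Descriptive statistics will be provided for all data collected". It adds generic tests for categorical and continuous variables, and names neither a safety population nor a safety analysis. Section VIII provides for event-by-event review: "The MSM will review Serious Adverse Events (SAEs) and will determine expectedness and causality of the event".

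**The concern.** Reinsertion is a post-randomisation event that may itself reflect how the bladder responded to the study procedure. Under this rule, the event that should prompt closer observation ends scheduled observation. These men then carry a second catheter for a period in which the study has no planned contact with them, although infection or further bladder symptoms in that period would be relevant to how the irrigation is tolerated.

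Two kinds of information are at stake. One is what happens between reinsertion and day 28. The other is the number of reinsertions in each arm. That count is informative in itself, yet the protocol uses reinsertion only as a reason for leaving. With about 60 men per arm, a handful of men can change a table of uncommon events. The point concerns safety data only. How these men enter the analysis of the endpoint is a separate question.

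**Working it through.** The documents give no reinsertion rate and no safety figure, so there is no stated number to reproduce. The check is a reading of the provisions together, followed by a rough scale.

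**1. Does follow-up stop?** No sentence says so. It follows from three things:
- the man is withdrawn from the study;
- adverse events are assessed only at scheduled visits;
- no contact after withdrawal is provided for.

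Study completion is not defined. I take it as Visit 4, the last scheduled contact.

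**2. How much is lost per man?** There are four scheduled assessments, and the loss depends on when reinsertion happens:
- before Visit 2: Visits 2, 3 and 4 are lost (3 of 4);
- between Visits 2 and 3: Visits 3 and 4 are lost (2 of 4);
- between Visits 3 and 4: Visit 4 is lost (1 of 4).

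The symptom questionnaire, which has an item on incomplete emptying, is scheduled at the same three visits and is lost with them.

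**3. Do other provisions fill the gap?**
- Reporting to the ethics board (Section IV) covers unanticipated problems. Inability to urinate is a listed risk and need not qualify.
- Close monitoring in Section IV is tied to the instillation and to catheter removal, not to the period after a new catheter.
- The Medical Safety Monitor reviews serious events, but no procedure is given for collecting them after withdrawal.
- The commitment to describe all collected data cannot reach data that were not collected.

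**4. Is the triggering event itself lost?** Not necessarily. A failed voiding trial occurs while the man is still enrolled and under study urologists, and no rule deletes his earlier data. What is missing is a requirement to record the reinsertion and to report it by arm.

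**5. Scale.** Inputs: 120 men, 60 per arm (Section VII). Assumption: the reinsertion rate lies within the 1% to 10% that Section IV gives for temporary inability to urinate, which is a different event.
- Men withdrawn = 120 × rate: 120 × 0.01 = 1.2; 120 × 0.10 = 12.
- Per arm = 60 × rate: 60 × 0.01 = 0.6; 60 × 0.10 = 6.
- Upper limit of assessments lost, with the highest rate and every reinsertion before Visit 2: 12 × 3 = 36, out of 120 × 3 = 360 planned after the treatment visit.

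**The case against.** The strongest reply is that the rule hides less than it seems to. Retention is seen by study urologists before withdrawal, adverse events are assessed at the treatment visit, and all collected data are to be described. Staff and the principal investigator monitor safety throughout, and institutional policy, which cannot be seen here, may cover events after withdrawal. The only objective is effectiveness and the only endpoint is infection at 48-72 hours. Few men are likely to be affected.

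Most of this stands, and it rules out several stronger readings that a reader might infer:
- **That retention disappears from the trial.** It can be recorded before the man leaves. Only the requirement to record and report it by arm is absent.
- **That the Medical Safety Monitor would not receive later serious events.** The documents support only that no route for collecting them is specified.
- **That a conclusion of safety would be biased in favour of irrigation.** The plan states no safety comparison or conclusion. Inability to urinate is listed under catheterisation, a risk both arms share, and no sentence links it to bladder irritation. Men may also be recatheterised for unrelated reasons, such as the urine-output monitoring mentioned in Section I. The direction is therefore unknown.
- **That the recorded irritation rate would be roughly halved.** One can suppose that 6 of 60 men (10%) have irritation and 3 of them are withdrawn, leaving 3/57 = 5.3% at Visit 2. But the share withdrawn has no source, and the cumulative count stays 6/60 if the irritation was noted before withdrawal.
- **That a difference in reinsertions could appear in no planned analysis.** The generic tests for categorical variables could cover it if it were recorded.

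The reply does not supply any scheduled safety contact after reinsertion, or any instruction to count reinsertions by arm.

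**Conclusion.** The concern holds in a limited form. A mandatory rule, followed as written, leaves men with a reinserted catheter without scheduled adverse-event assessment from reinsertion to day 28, and does not oblige the trial to record or report reinsertions by arm. Because reinsertion follows randomisation and could be affected by the instillation, the loss may differ between arms.

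The end of follow-up is inferred from the withdrawal rule and the absence of any later contact; it is not stated. The size rests on an assumed rate of 1% to 10%, or about 1 to 12 of 120 men, each losing between one and three of four assessments. The direction of any distortion cannot be determined. This is a worthwhile, inexpensive improvement to what the trial observes; the planned endpoint test and the sample size do not depend on it.

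**What to change.** In Section III, separate leaving endpoint assessment from leaving safety follow-up. State that a man with a reinserted catheter keeps the adverse-event assessments at his remaining visits through day 28, by phone if necessary, unless he withdraws consent. Require each reinsertion to be recorded with its date and reason. In Section VII, add a descriptive table of reinsertions and adverse events by assigned arm in all randomised men. No formal test is needed, since the plan has no safety hypothesis.

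The change concerns data collection and reporting only and leaves the clinical decision to reinsert untouched. It costs a short amendment, one table and a few phone contacts: at the assumed upper rate, at most 12 × 3 = 36, all at time points already in the schedule. Visits 3 and 4 are already phone calls, so no new procedure, staff or sample-size change is involved.

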A Randomized Trial of Betadine Bladder Irrigations vs. Standard of Care Prior to Indwelling Catheter Removal to Reduce Bacteriuria and Catheter-Associated Urinary Tract Infections

Principal Investigator

[name] MD

Co-Investigators

[name] MD [name] MD [name] MD [name] MD [name] RN

PROTOCOL DATE: SEPTEMBER 26, 2018

TABLE OF CONTENTS

I.	BACKGROUND AND RATIONALE	2
II.	Objectives and Endpoint	3
III.	Methodology	3
IV.	Risks and Benefits	6
V.	ELIGIBILITY CRITERIA	7
VI.	DATA ANALYSIS	8
VII.	DATA SAFETY MONITORING PLAN	10
VIII.	References	11
APP	ENDIX A: QUESTIONNAIRE	12

I. BACKGROUND AND RATIONALE

Indwelling urinary catheters are routinely used in the care of hospitalized patients for a variety of reasons, including monitoring of urine output in critically ill patients, relief of urinary obstruction, and prevention of contamination of decubitus ulcers. Bacteriuria increases by 3-10% each day a catheter is left in place^{1, 2} meaning that by 30 days, generally 100% of patients with indwelling catheters will have bacteria in their urine. The majority of these people do not have urinary tract infections (UTIs), they are merely colonized and do not require treatment.

Over the last decade, there has been great emphasis on reducing the incidence of hospitalacquired infections, including catheter-associated UTI (CAUTI). Hospitals have had relatively good results, though there is certainly still room for improvement. To define a standard (and ultimately to compare hospitals against each other), a surveillance definition for CAUTI³ has been developed by the National Healthcare Safety Network (NHSN). While useful for surveillance, the definition does not correlate with clinical UTIs, leading to over diagnosis and over-reporting of UTIs (in other words, those with merely bladder colonization being diagnosed as having a UTI). Despite continuing progress in standard methods of reducing infection rates (including decreasing the number of catheters inserted, ensuring proper catheter maintenance, and removing catheters when no long necessary) we continue to have unacceptably high rates of CAUTIs. As hospital-acquired infection rates are increasingly tied to reimbursement from governmental agencies, there is a great need to reduce infection, either by meeting surveillance criteria or through novel clinical approaches.

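### The sample size rests on bacteriuria figures labelled as infection, so the stated 80% power is not shown to apply to the CAUTI endpoint

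*Combined protocol and SAP*

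**What the plan says.** Section VII (Data Analysis) gives the control rate as "An infection rate of 25% is anticipated at day 2 post catheter removal for the SOC group". It takes the effect from an earlier study: "A difference has been shown of a 75% drop in infection rate using povidone-iodine bladder irrigation". From these, the power analysis "yields 55 patients needed in each arm to have 80% power at a 0.05 significance level to detect a difference of 25% versus 6.25" (the last figure is a percentage). The same section then applies Fisher's exact test to presence or absence of bacteriuria at 48-72 hours.

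Section II (Objective and Endpoint) names a different event: NHSN-defined CAUTI at 48-72 hours, assessed by urinalysis, culture and a symptom questionnaire.

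Section I (Background and Rationale) states "Bacteriuria increases by 3-10% each day a catheter is left in place". It adds that most catheterized patients with bacteria in the urine are colonized and have no UTI. It reports the study behind the 75% figure as having sterilized the urine of 75% of patients, and says that neither this study nor its companion examined CAUTI rates.

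Section IV (Risks and Benefits) lists UTI among the risks of catheterization under "Less Frequent (occurring from 1% to 10% of the time". The entry gives no arm, time point, catheter duration or definition.

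**The concern.** Three words (infection, CAUTI, bacteriuria) stand for what should be one endpoint. The sample-size paragraph uses the first, the endpoint statement the second and the test the third. If the 25% and the 75% drop are bacteriuria figures, the power calculation supports a bacteriuria comparison and says nothing about CAUTI.

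What is at stake is the conclusion the trial may draw. With CAUTI as the stated endpoint, readers will take 80% power as power for CAUTI. If CAUTI is much rarer than bacteriuria, a null CAUTI result would say little. A positive bacteriuria result could also be reported as if it were the CAUTI result.

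**Working it through.** **Step 1. Reproduce the plan's figure.** Inputs from Section VII: p1 = 0.25, p2 = 0.25 × (1 − 0.75) = 0.0625, 80% power, alpha 0.05. Allocation is 1:1 (Section III). Sidedness is not stated, so two-sided is assumed. With unpooled variance:

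n = (1.960 + 0.842)² × [p1(1 − p1) + p2(1 − p2)] / (p1 − p2)²
= 7.849 × (0.1875 + 0.0586) / 0.03516 = 54.9, so 55 per arm.

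The stated size follows from the stated rates. The question is which event the rates describe.

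**Step 2. Trace the two inputs.**

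| Input | Name in Section VII | What the rest of the protocol supports |
|---|---|---|
| 75% drop | infection rate | Urine sterilization in the cited study; Section I says CAUTI was not studied there |
| 25% control rate | infection rate | No citation and no definition; the section's own test is on bacteriuria |

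**Step 3. Is 25% plausible as bacteriuria?** Inputs: 3-10% per catheter day (Section I) and at least 5 catheter days (Section VI).

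- Compounded: 1 − 0.97⁵ = 14% and 1 − 0.90⁵ = 41%.
- Added linearly: 5 × 3% = 15% and 5 × 10% = 50%.

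The 25% lies inside both ranges. This shows consistency, not proof. The calculation covers the catheterized period at its minimum length, not status 48-72 hours after removal, and the ranges are wide.

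**Step 4. Is there any support for 25% as CAUTI?** None is given. The only other UTI frequency in the protocol is the 1-10% band in Section IV. In 55 standard-care men, 25% means 0.25 × 55 = 13.75 events, while the band means 0.55 to 5.5.

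**Step 5. How far could power fall? (Illustration only.)** Suppose the CAUTI control rate were at the top of that band and the 75% drop carried over to CAUTI. Both are assumptions that the documents do not make. Fisher powers are exact enumerations at 55 per arm, two-sided 0.05.

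| Control vs Betadine | Fisher power |
|---|---|
| 25% vs 6.25% (plan) | 72% |
| 10% vs 2.5% | 19% |
| 5% vs 1.25% | 3% |

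The like-for-like fall at 10% is from 72% to 19%, because the plan's 80% comes from a normal approximation and not from the Fisher test. At 10% versus 2.5%, the formula in Step 1 would need 7.849 × (0.09 + 0.024375) / 0.075² = 159.6, so 160 per arm (163 with pooled variance).

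**The case against.** The best defence is that nothing here is contradictory. The 55 per arm reproduces. The objective in Section II presents bacteriuria as the route to CAUTI. Section I says the NHSN definition over-diagnoses, counting some colonized patients as infected, so the surveillance CAUTI rate could sit well above the clinical UTI rate and nearer to bacteriuria. On that view 25% might be a fair CAUTI rate, and putting the Section IV band in its place is unwarranted.

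Much of this stands. The band is generic and is not the endpoint's control rate, so 19% and 3% are illustrations and not estimates of this trial's power. The 14-41% range cannot by itself identify what 25% measures. The defence does not, however, supply a basis for 25% as CAUTI, or for carrying a sterilization result over to CAUTI.

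A reader might also infer three stronger points, which the documents do not support:

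- **Two incompatible rates for one event.** Section IV describes UTI as a general catheterization risk, and Section VII gives a control rate for the trial endpoint. Clinical UTI at 1-10% and endpoint positivity at 25% can both be true.
- **A safety alarm.** At a 10% rate, 14 or more events in 55 has probability 0.0008, but no rule in the plan makes that comparison. Section VIII has the Medical Safety Monitor review serious adverse events, where the monitor "will determine expectedness and causality of the event". It sets no UTI count or rate threshold and does not refer to the band. Nor does it make a positive research culture a serious adverse event.
- **Participants told too low a risk.** The consent text is not among the documents, so what participants are told cannot be judged.

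**Conclusion.** The point holds in a limited form. Section VII presents as infection rates two figures that the protocol supports only as bacteriuria, while Section II makes CAUTI the endpoint. The stated 80% power is therefore not shown to apply to CAUTI.

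The loss of power for CAUTI cannot be sized from the documents, because they give no CAUTI control rate. If that rate were 10% and the 75% drop held, Fisher power at 55 per arm would be about 19%.

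The conclusion rests on the Background's own account of the cited study and of colonization, and on the test named in Section VII. It does not depend on the Section IV band. It does not say that 25% is wrong as a bacteriuria rate, or that the sample-size arithmetic fails for the rates stated.

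**What to change.** Before outcomes are compared between arms:

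1. In Section VII, call 25% and 6.25% bacteriuria rates, give the basis for 25%, and describe the 75% as a urine-sterilization result.
2. State there that the sample size and power apply to bacteriuria at 48-72 hours only.
3. Make Section II agree: bacteriuria at 48-72 hours as the primary endpoint, with NHSN-defined CAUTI reported descriptively as a secondary outcome.
4. Add one sentence distinguishing the general UTI risk in Section IV from the planning rate in Section VII.

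This needs no additional patients or procedures. It is more than an edit, though: it changes the status of CAUTI in Section II, and the trial's claim about CAUTI becomes more modest. Keeping CAUTI primary would instead require a sourced CAUTI control rate and effect, a test on CAUTI, and a new sample size.

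Relabelling does not address the gap between 80% and the 72% Fisher power at the planned rates, which is a separate matter.

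### The 80% power stated for 55 per arm is not delivered by the Fisher's exact test named for the endpoint, which gives about 72% (about 70% after the plan's own 10% dropout)

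*Combined protocol and SAP*

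**What the plan says.** All the relevant text is in Section VII (Data Analysis).

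- **Planning rate.** "An infection rate of 25% is anticipated at day 2 post catheter removal for the SOC group". A 75% relative reduction brings this to 6.25% with povidone-iodine.
- **Sample size.** The power analysis "yields 55 patients needed in each arm to have 80% power at a 0.05 significance level". The formula or test behind it is not named, and sidedness is not given.
- **Dropout.** "We estimate at most a 10% dropout rate and plan to enroll 60 patients per arm to account for this".
- **Test for the endpoint.** Bacteriuria at 48-72 hours "will be examined with a Fisher's exact tests, odds ratio and 95% confidence intervals".
- **General rule for other categorical data.** "The categorical variables will be examined using Pearson's Chi-square tests where appropriate (expected frequency >5), otherwise Fisher's exact tests will be used".

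Section III (Methodology) gives 1:1 allocation and a total of 110 men, with up to 120 enrolled so that enough complete the 48-72 hour visit.

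**The concern.** A power figure describes a particular test. Fisher's exact test conditions on the total number of events, and with about 17 events expected over both arms its p-value can take only a few values. Its true type I error then falls well below 5%, and power falls with it. A sample size from a large-sample formula will not carry over to it.

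What is at stake is how the trial will be read. This is one small study with one declared endpoint. If the real chance of a false negative is nearer 30% than 20%, a non-significant result says less against the irrigation than readers of the plan would think. The shortfall comes only from the choice of test, so it can be avoided at no cost in patients.

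**Working it through.** **Inputs (Section VII unless noted).** SOC rate p1 = 0.25; irrigation rate p2 = 0.25 × (1 − 0.75) = 0.0625; alpha 0.05; target power 80%; 1:1 allocation (Section III); 60 enrolled per arm; dropout at most 10%. A two-sided test is assumed, because the plan does not say.

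**1. Reproduce the 55.** Two-sided normal approximation with unpooled variance:

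n = (z₀.₉₇₅ + z₀.₈₀)² × [p1(1−p1) + p2(1−p2)] / (p1−p2)²

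= (1.960 + 0.842)² × (0.1875 + 0.0586) / 0.1875² = 7.849 × 0.2461 / 0.03516 = 54.94, so 55.

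The plan's number is right for that formula. The pooled-variance version gives 58, and the continuity-corrected version, which tracks Fisher's test more closely, gives 68.

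**2. Exact power.** For each test, power = Σ Bin(i; n, 0.25) × Bin(j; n, 0.0625), summed over all tables (i, j) with two-sided p ≤ 0.05. At n = 55 this runs over 56 × 56 tables.

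| Evaluable per arm | Fisher | Pearson, uncorrected | Mid-p Fisher |
|---|---|---|---|
| 54 | 70.5% | 79.6% | 78.2% |
| 55 | 71.6% | 80.4% | 79.0% |
| 60 | 76.6% | 83.3% | 83.0% |
| 63 | 79.3% | 85.2% | 85.1% |
| 64 | 80.1% | 85.8% | 85.7% |

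Boschloo's unconditional exact test gives 79.0% at 55. With equal arms, Fisher first reaches 80% at 64 per arm.

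**3. Why they differ.** Take 10 events against 3 with 55 per arm. Pearson: z = (7/55) / √(2 × 0.1182 × 0.8818 / 55) = 0.1273 / 0.0616 = 2.07, p = 0.039. Fisher: p = 0.073. Fisher needs 11 against 3 (p = 0.042).

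**4. Type I error at n = 55.** At the common rate (25% + 6.25%)/2 = 15.6%, Fisher rejects 2.5% of the time and Pearson 5.0%. Over all common rates, Pearson peaks at about 5.3% and Boschloo at 4.7%.

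**5. Dropout.** 60 × 0.9 = 54, not 55. Keeping 55 needs 55/0.9 = 61.1, so 62 enrolled per arm. Alone this costs about one point of Fisher power (71.6% to 70.5%).

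**6. The general rule.** Expected events per arm under a common rate are 55 × 0.156 = 8.6, which is above 5. The section's rule for other categorical variables would therefore select Pearson's chi-square.

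**7. Unequal arms.** Fisher's two-sided power is uneven when arm sizes differ slightly. With 54 SOC and 55 irrigation patients it is 77.4%; with 55 and 54 it is 72.4%. Both are below 80%. A few splits with more than 55 in both arms do reach it (57 SOC and 58 irrigation: 80.1%), but the plan cannot count on these.

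**The case against.** **The 55 is not a miscalculation.** This stands. It follows from the plan's inputs and is correct for an uncorrected chi-square test. The fault is that the plan analyses with a different test from the one it was sized for.

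**Sidedness is not stated, and a one-sided 0.05 Fisher test would have 82.6% power at 55 and 81.8% at 54.** True, so the conclusion rests on a two-sided reading. That is the natural one: the two-sided formula returns 55 where its one-sided counterpart returns 44 (43.3 rounded up), and the test is paired with 95% confidence intervals. Nothing in the text points to one-sided testing.

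**Dropout is a maximum, so 70% is the low end.** Fair. With equal arms the range is 70.5% (54 evaluable) to 76.6% (all 60), and no equal split in that range reaches 80%.

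**Fisher's test is legitimate, and the specific sentence overrides the general rule.** Both points stand. Only 55 × 0.0625 = 3.4 events are expected in the irrigation arm, and a conservative test does not invalidate the comparison. The general rule shows only that chi-square is already acceptable to the plan at these counts. If Fisher is kept, the power statement has to change.

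**The planning rates matter as much as the test.** With the 75% reduction kept and 55 per arm, Fisher power is 57% if the SOC rate is 20% and 82% if it is 30%; Pearson gives 69% and 89%. This is a separate uncertainty. The mismatch is present at the plan's own rates.

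**The alternatives are not perfect.** Also true. Pearson can slightly exceed 5%, mid-p and Boschloo fall one point short at 55, and at 54 Pearson and mid-p are both just under 80%. These gaps are small beside Fisher's eight to nine points.

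**Conclusion.** The stated power is wrong for the named analysis. At 25% versus 6.25%, two-sided Fisher's exact test has 71.6% power with 55 per arm and 70.5% with the 54 per arm that the plan's own dropout allowance leaves. The miss rate is 28-30% rather than 20%. Nearly all of the loss comes from the test; the one-patient rounding in the dropout step adds about a point.

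This assumes a two-sided 0.05 test, equal evaluable arms, and that the planning rates describe the outcome tested. The last assumption needs its own reconciliation: Section II declares NHSN-defined CAUTI as the endpoint, while Section VII calls the planning rates infection rates and applies the test to bacteriuria. Validity is not in question, since Fisher's test controls type I error; what fails is the power claim.

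**What to change.** Amend Section VII before outcome data are seen, so that a change of test cannot look data-driven. Choose one of these:

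1. **Change the test (preferred).** Name a two-sided Pearson chi-square test without continuity correction as the primary test, with exact power of 80.4% at 55 and 79.6% at 54 per arm. If type I error must stay at or below 5%, name Boschloo's test instead (79.0% at 55, maximum size 4.7%). Mid-p Fisher has the same power at 55.
2. **Keep Fisher and restate the power.** Give it as about 72% with 55 and 70% with 54 evaluable per arm.

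If the sponsor wants both Fisher and 80%, that takes 64 evaluable per arm, or 64/0.9 = 71.1, so 72 enrolled. This is the only route that needs more patients.

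In the same edit, state that the test is two-sided, name the method behind the sample size, and say that 10% dropout from 60 leaves 54 evaluable per arm.

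The cost of option 1 or 2 is about one sentence and no patients. Option 2 also means publishing a less favourable power figure.
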